8.3.3.6. Physical Examination

Physical examination will consist of full and routine examinations:

Full physical examination will include abdominal, cardiovascular, general appearance, head, eyes, ears/nose/throat, lymph nodes, musculoskeletal, neck, neurological, dermatological, respiratory and other.

Routine physical examinations will include abdominal, cardiovascular, general appearance, respiratory, neurological, and other.

The full examination will be performed on Day 1 and at week 48 and the routine examination will be performed at week 24.

If any significant abnormality started prior to informed consent, it will be recorded in corresponding medical history. If any significant abnormality started after informed consent, it will be recorded as a corresponding event on AE form.

8.3.3.7. Body Weight

Body weight will also be measured as safety parameter and recorded in pounds or kilograms.

Criteria for Potentially Clinically Significant Values (PCSV) for Body Weight⁷:

The following criteria for body weight PCSV will be defined:

- Body Weight at post-baseline >=5% increase from baseline
- Body Weight at post-baseline >=5% decrease from baseline

8.4. Analysis Visit Definitions

The acceptable visit dates windows of observation, examination, and investigation are specified as in Table 5: The analysis visit windows. Data obtained within the acceptable windows will be used for analysis or presentation. If the dates of observation, examination, or investigation are out of the following acceptable range, data obtained on those days will not be used for analysis or summary statistics. However, all data as captured will be listed. The date of the first dose of study drug in MT-1186-A04 is defined as A04 Day 1. Unless otherwise specified, baseline will be the last observed value of the parameter of interest prior to the first intake of study drug in MT-1186-A02 (this includes unscheduled visits). For other visits, if there are multiple data in a window, the closest data to nominal day will be used. If the distance to the nominal day is the same, the data of later date will be used.

Mitsubishi Tanabe Pharma America, Inc.

Table 5: The analysis visit windows

Analysis visit	Nominal day	Window		
		Except for laboratory test in Japan site	Laboratory test in Japan site	
Day 1 (A02)	Day 1	≤Day 1		
Day 8 (A02)	Day 8	-	Day 2 to 11	
Week 4 (A02)	Day 29	Day 2 to 42	Day 23 to 42	
Week 8 (A02)	Day 57	Day 43 to 71		
Week 12 (A02)	Day 85	Day 72 to 127		
Week 24 (A02)	Day 169	Day 128 to 211		
Week 36 (A02)	Day 253	Day 212 to 294		
Week 48	Day 337	Day 295 to 379		
(A02 and A04 Day 1)				
Week 60 (A04 Week 12)	Day 421	Day 380 to 462		
Week 72 (A04 Week 24)	Day 505	Day 463 to 546		
Week 84 (A04 Week 36)	Day 589	Day 547 to 630		
Week 96 (A04 Week 48)	Day 673	Day 631 to 715		

In case assessments are done at the Early Termination visit, these assessments will be used as data for the scheduled visit closest to the early termination time point, in case the corresponding data are missing from this visit.

Mitsubishi Tanabe Pharma America, Inc.

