9.3.3. Laboratory Tests

Only central laboratory data and change from baseline (haematology, biochemistry or urinalysis) will be summarized with descriptive statistics (continuous variables) or as distributions (categorical variables) by visit except for pregnancy test parameter. For urinalysis parameter, a shift table from baseline will be presented.

The categories for out of reference range will be Low, Normal and High for Hematology, Biochemistry, Urinalysis and , and Normal and Abnormal for Urinalysis (Qualitative Value). For these categories, a shift table from baseline to each visit up to A04 Week 96 will be presented.

Laboratory test values will be considered potentially clinically significant (PCS) if they meet either the low or high PCSV criteria listed in section 8.3.3.3. A shift table describing the number and percentage of subjects shifting from non PCSV at baseline to PCSV at post-baseline will be performed any time during treatment period.

The percentages will be calculated from the number of subjects with available baseline values and any time post-baseline value.

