10.3. Analysis Visits to Report

Efficacy:

Analysis Visit	Apply to		
Parameter	CAFS	ALSFRS-R	%SVC
	ÅLSAQ-40		Body Weight
Screening		X	X
Baseline (A02 Day 1)		X	X
Week 4 (A02)		X	X
Week 8 (A02)		X	X
Week 12 (A02)		X	X
Week 24 (A02)	X	X	X
Week 36 (A02)		X	X
Week 48 (A02 and A04	X	X	X
Day 1)			
Week 60 (A04 Week 12)		X	
Week 72 (A04 Week 24)	X	X	X
Week 84 (A04 Week 36)		X	
Week 96 (A04 Week 48)	X	X	X

Safety:

Analysis Visit	Apply to			
	Laboratory Tests	Vital Signs	12-Lead ECGs	C-SSRS
Screening	X	X	X	X
Baseline (A02	X	X	X	X
Day 1)				
Day 8 (A02)	X (only for Japan)			
Week 2 (A02)				
Week 4 (A02)	X	X		X
Week 8 (A02)	X	X	_	
Week 12 (A02)	X	X		X
Week 16 (A02)				
Week 20 (A02)				
Week 24 (A02)	X	X	X	X
Week 36 (A02)	X	X		
Week 48 (A02	X	X	X	X
and A04 Day 1)				
Week 72 (A04)	X	X	X	X
Week 96 (A04)	X	X	X	X

Mitsubishi Tanabe Pharma America, Inc.

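### SAP Table 5 has no analysis window for Japanese laboratory results on Days 12 to 22, so section 8.4 excludes them from analysis

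*SAP*

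**What the plan says.** SAP 8.4 assigns each assessment to an analysis visit through the windows in Table 5. The rule for anything outside them is: "If the dates of observation, examination, or investigation are out of the following acceptable range, data obtained on those days will not be used". The exclusion covers both analyses and descriptive summaries. The next sentence of 8.4 keeps such values in the listings: "However, all data as captured will be listed".

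Table 5 has two window columns, one for laboratory tests at Japanese sites and one for everything else. In the Japan column, Day 8 covers Days 2 to 11 and Week 4 covers Days 23 to 42. In the other column there is no Day 8 visit, and Week 4 covers Days 2 to 42. From Week 8 on, a single window is given per visit.

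Two further rules in 8.4 bear on the point. Within a window, "if there are multiple data in a window, the closest data to nominal day will be used", with ties going to the later date. For early-termination visits, "these assessments will be used as data for the scheduled visit closest to the early termination time point", provided that visit has no data of its own.

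SAP 9.3.3 summarizes central-laboratory data by visit and tabulates shifts from baseline to each visit. It adds a table, covering the whole treatment period, of shifts to potentially clinically significant values (PCSV): "A shift table describing the number and percentage of subjects shifting from non PCSV at baseline to PCSV at post-baseline will be performed any time". SAP 10.3 marks a Day 8 laboratory test for Japan only and leaves the Week 2 row blank.

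**The concern.** A visit-window table should place every post-baseline day in exactly one window unless the plan says why not. Here an interval early in treatment belongs to none, for one country and one type of data, and neither 8.4 nor section 11 (changes from the protocol) gives a reason. Combined with the exclusion rule, valid post-baseline safety values would be discarded at Japanese sites.

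Two outputs are at stake:

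- **By-visit summaries and shift tables.** If the scheduled Week 4 sample is missing, a value from Days 12 to 22 can stand in for it at a non-Japanese site but not at a Japanese one.
- **The any-time PCSV table.** This table is meant to catch an abnormality whenever it occurs. Read literally, 8.4 removes a Japanese value from Days 12 to 22 before the table is built. A central-laboratory repeat in the second or third week, after an abnormal Day 8 result, is the kind of sample affected.

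Under SAP 5.2 the final analysis will not be conducted, so the interim analysis is the only one, and no later analysis would put this right.

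**Working it through.** The plan states no figure to reproduce. The check compares the windows with the calendar.

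**Inputs (SAP Table 5).** Nominal days: 8 (Japan laboratory only), 29, 57, 85, 169, 253, 337, 421, 505, 589, 673. Windows for all other data: 2–42, 43–71, 72–127, 128–211, 212–294, 295–379, 380–462, 463–546, 547–630, 631–715. Japan laboratory: 2–11 and 23–42, then the common windows. The blank Japan cells from Week 8 on are read as sharing the common window; this is an assumption about the table's layout.

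**1. Coverage, Days 2 to 715.**

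| Column | Days in no window | Overlaps |
|---|---|---|
| All other data | none | none |
| Japan laboratory | 12 to 22 | none |

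**2. Size of the gap.** 22 − 12 + 1 = 11 days. Days 2 to 42 are 42 − 2 + 1 = 41 days. 11/41 = 26.8%. This is a share of calendar days, not of results; the documents give no count of affected results.

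**3. The table's own convention.** The midpoints of adjacent nominal days from Day 29 on are 43, 71, 127, 211, 295, 379, 463, 547 and 631. The printed cut-points are 42/43, 71/72, 127/128, 211/212, 294/295, 379/380, 462/463, 546/547 and 630/631. Each lies at the midpoint, with the midpoint day going to one side or the other. Only the cut between Day 8 and Day 29 departs from this.

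**4. What the convention gives here.** (8 + 29)/2 = 18.5, so Day 8 = Days 2 to 18 and Week 4 = Days 19 to 42. By distance, Day 18 is 10 days from Day 8 and 11 from Day 29; Day 19 is 11 from Day 8 and 10 from Day 29.

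**5. A possible origin.** Nominal days follow 7 × week + 1, so a Week 2 visit would be Day 15. Its midpoints with its neighbours are (8 + 15)/2 = 11.5 and (15 + 29)/2 = 22. The convention would give it Days 12 to 22, which is exactly the gap. SAP 10.3 still carries a Week 2 row with nothing marked. The blank Week 16 and Week 20 rows also have no window, but there the neighbouring windows meet (72–127 and 128–211). This is consistent with a Week 2 window removed without closing up its neighbours. It is an inference; the documents do not say so.

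**6. What happens to a central-laboratory value from Days 12 to 22 under 8.4.**

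| Situation | Japanese site | Other site |
|---|---|---|
| By-visit tables, a closer Week 4 sample exists | not used | not used (closest to Day 29 wins) |
| By-visit tables, no closer sample in the window | not used | used as Week 4 |
| Early-termination sample, closest visit has no data | reassigned to that visit | reassigned to that visit |
| Any-time PCSV table | excluded if 8.4 applies | depends on whether the table uses all values or one selected per visit |
| Listings | listed | listed |

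The sites differ in the second row, and in the fourth if 8.4 governs that table while all in-window values are used.

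**The case against.** The strongest reply is that the gap hardly matters.

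- **Little falls in it.** SAP 10.3 marks Japanese laboratory tests at Day 8 and Week 4 and none at Week 2. Repeats on Days 9 to 11 are inside the Day 8 window. Section 9.3.3 summarizes central-laboratory data only, so a local repeat is out in any case. This stands and limits the size.
- **Safety information is not lost.** All values are listed, early-termination samples can be reassigned, and Protocol 15.5 has clinically significant laboratory abnormalities recorded as adverse events, which can reach the tables in SAP 9.3.1. This stands.
- **The contrast between countries is narrower than it looks.** A reader might infer that the same result elsewhere always counts as Week 4. The closest-to-nominal rule does not support that: with a scheduled sample nearer Day 29, the earlier value drops out of by-visit tables at every site. For the same reason, closing the gap changes those tables only when the scheduled sample is missing.
- **Exclusion from the PCSV table is not explicit.** That table is to be produced "will be performed any time during treatment period", and 9.3.3 does not restrict it to windowed values. The general wording of 8.4 points to exclusion, but the SAP does not settle it. What stands is an ambiguity under which two programmers could produce different counts.
- **The bounds may be deliberate.** The Japan column was written separately, and these are MT-1186-A02 visits whose own SAP and Japan-specific schedule are not available here. Contiguity everywhere else, and the exact match to a Week 2 window, make an oversight more likely but do not prove one.

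**Conclusion.** The point holds as a defect in the table with a limited consequence. Days 12 to 22 are in no window for Japanese laboratory tests, and 8.4 as written discards values from those days in by-visit summaries and shift tables, even when nothing else represents the visit. Whether the any-time PCSV table also loses them is unsettled; a literal reading of 8.4 says yes.

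The gap is 11 consecutive days, 27% of the calendar from Day 2 to Day 42. The number of results affected is unknown and probably small.

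A reader might go further and infer a treatment bias in the safety comparison. The documents do not support that: the gap is the same in both arms, and randomization was stratified by region.

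The conclusion assumes that Table 5 is printed as intended and that the blank Japan cells from Week 8 on share the common windows. It is a minor correction, worth making because the rule is wrong as written and costs almost nothing to repair.

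**What to change.** 1. Check the Japan-specific schedule and the MT-1186-A02 windows to see whether a Week 2 laboratory test was planned in Japan.
2. If it was not, make the Japan column contiguous by the table's own midpoint convention: Day 8 = Days 2 to 18, Week 4 = Days 19 to 42. If it was, restore a Week 2 window of Days 12 to 22 (nominal Day 15) and leave the two neighbouring windows alone. The sponsor should confirm the intended bounds.
3. Add one sentence to SAP 9.3.3 stating that the any-time PCSV tables use all post-baseline central-laboratory values during the treatment period, regardless of visit window. This matters more than the window bounds, because closing the gap alone would still let a scheduled sample displace a repeat if that table were built from one value per visit.

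The cost is two numbers or one added row in Table 5, one sentence in 9.3.3, and a consistency check against the MT-1186-A02 windows. The downside is that a sample taken as late as Day 18 would be labelled Day 8. If the MT-1186-A02 analysis used different bounds, early by-visit laboratory tables could also differ slightly between the two reports, and the report should say so.

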9. STATISTICAL METHODOLOGY

9.1. Study Subjects

9.1.1. Subject Disposition

Subject disposition will be summarized by treatment group using descriptive statistics. The percentages will be calculated based on the number of randomized subjects, unless otherwise specified. In addition, all subjects who completed study MT-1186-A02 will be listed.

- The number of subjects randomized to study MT-1186-A02 (i.e. the number of subjects in the Randomized set)
- The number (%) of subjects completed MT-1186-A02 and signed ICF for MT-1186-A04
- The number (%) of subjects eligible for MT-1186-A04
- The number (%) of subjects who failed eligibility criteria (% calculated from the subjects completed MT-1186-A02 and signed ICF for MT-1186-A04), including the distribution of reasons for screen failure
- The number (%) of subjects who completed the treatment period in MT-1186-A04
- The number (%) of subjects who discontinued treatment during MT-1186-A04 including the distribution of reasons for treatment discontinuation in MT-1186-A04
- The number (%) of subjects who completed MT-1186-A04 study
- The number (%) of subjects who discontinued MT-1186-A04 study including the distribution of reasons for study discontinuation
- The number (%) of subject who entered to the safety follow-up period in MT-1186-A04

9.1.2. Demography

Demographics and baseline characteristics will be listed and summarized descriptively by treatment group for Randomized set. All parameters described in Table 2 will be used for the analysis.

9.1.3. ALS History

ALS History will be listed and summarized descriptively by treatment group for all Randomized and FAS. All parameters described in Table 3 will be used for the analysis.

9.1.4. Intercurrent Events (ICEs) Distribution

ICEs distribution will be summarized by treatment group using descriptive statistics for the Randomized set:

- The number (%) of subjects with ICE1 of Additional/new AMX0035 treatment occurred during MT-1186-A02 and MT-1186-A04
- The number (%) of subjects with ICE2 of Death event occurred during MT-1186-A02 and MT-1186-A04

Mitsubishi Tanabe Pharma America, Inc.

9.1.5. Protocol Deviations

Protocol deviations which occurred during only MT-1186-A04 will be listed and the major protocol deviations occurred during only MT-1186-A04 will be summarized.

9.1.6. Concomitant Medications

All concomitant medications taken during only MT-1186-A04 will be listed and those occurred during MT-1186-A02 and MT-1186-A04 summarized by treatment group for the FAS. Separate summaries of permitted concomitant medications, (riluzole and AMX0035), will be presented in tabular form using the ATC Level 4 and preferred term. Other concomitant medications will be presented in tabular form using the ATC Level 1, ATC Level 2, and PT. Frequencies and percentages of subjects receiving medications will be presented. The tables will be sorted by overall descending frequency of ATC Level(s) and then, within an ATC Level, by overall descending frequency of PT.

9.1.7. Study Medication Exposure and Compliance

Study medication exposure during MT-1186-A02 and MT-1186-A04 will be calculated as specified in section 8.3.1.4. The following information will be listed and summarized by treatment group for the FAS:

- The number of subjects exposed to study treatment
- The number of subjects exposed to study treatment by oral administration
- The number of subjects exposed to study treatment by PEG/RIG administration
- Total duration of exposure to study treatment (days)
- Total exposure to study treatment, expressed as person years (sum of exposure to study treatment)
- Total duration of exposure (days) under PEG/RIG administration
- Time to date subjects switched to PEG/RIG administration

Treatment compliance will be determined by performing study treatment accountability of returned study treatment used and unused according to section 8.3.1.4. Treatment compliance will be summarized and listed for the FAS using descriptive statistics. Non-compliance is defined as taking < 80% or > 120% of study medication during evaluation periods. The proportions of subjects with non-compliance as defined above will be summarized and listed for the FAS.

Mitsubishi Tanabe Pharma America, Inc.

9.2. Efficacy Analysis

For efficacy endpoints, data from MT-1186-A02 and MT-1186-A04 will be descriptively summarized and data from MT-1186-A04 only will be listed.

Survival endpoints and the other efficacy endpoints will be performed on the Randomized set and the FAS respectively. For the latter, all available assessments from both MT-1186-A02 and MT-1186-A04 will be included in the statistical models and the estimates and 95% CI will be presented at each available time point, unless other specified.

All available data regardless of use of additional/new AMX0035 treatment (ICE1) drug (except for the secondary estimand) and all available regardless of early discontinuation will be included.

[figure not shown]
9.2.1. Primary Endpoint

9.2.1.1. Primary Analysis

The primary efficacy endpoint (TIMETO) is Time from the randomization date in Study MT-1186-A02 to at least a 12-point decrease in ALSFRS-R or death, whichever happens first. All available event data regardless of use of additional/new AMX0035 treatment (ICE1) drug will be included. This endpoint will be summarized using the number of events and percentages and displayed by Kaplan-Meier estimates stratified by treatment group. The comparison between Treatment Group 2 versus Treatment Group 1 will be performed using stratified log rank test with stratifications factors used during MT-1186-A02 randomization:

- ALSFRS-R decline rate (DR) score from the MT-1186-A02 screening period (2 levels strata of -1,-2 or -3,-4)
- Geographical region (GR) 3 levels strata of Europe, America, or Asia Pacific.

This statistical test will be done as 2-sided with a nominal 20% significance level. The SAS code planned for the analysis is outlined below.

The primary efficacy endpoint (TIMETO) will also be analyzed using the Cox Proportional Hazard Model with terms for treatment (TRTP) as explanatory variable and baseline ALSFRS-R score (BASE), and the MT-1186-A02 randomization strata as covariates (DR and

Mitsubishi Tanabe Pharma America, Inc.

GR). This statistical test will be done as 2-sided with a nominal 20% significance level. Point estimates of treatment differences will be accompanied with 2-sided 80% CIs.

The SAS code planned for the analysis is outlined below.

[figure not shown]
Individual Component Analysis

To investigate the effect on the individual component for the primary endpoint,

- Time from the randomization date in Study MT-1186-A02 to at least a 12-point decrease in ALSFRS-R
 - ➤ Change in ALSFRS-R Total Score at time the event occurred
 - > Change in ALSFRS-R Bulbar Function Score at time the event occurred
 - ➤ Change in ALSFRS-R Limb Function Score at time the event occurred
 - > Change in ALSFRS-R Respiratory Function Score at time the event occurred
- Time from the randomization date in Study MT-1186-A02 to death

The above parameters will be descriptively summarized.

9.2.1.3. Additional Supportive Analyses Addressing the Secondary Estimand				
_				
"				
			_	

Statistical Analysis Plan
Study No. MT-1186-A04

Mitsubishi Tanabe Pharma America, Inc.

[figure not shown]
9.2.2. Secondary Efficacy Endpoints

[figure not shown]
The following Secondary endpoints will be analyzed without adjustment to Type I error and no pre-specified order. All p-values will be nominally displayed. All available data regardless of use of additional/new AMX0035 treatment (ICE1) drug will be included.

[figure not shown]
9.2.2.1.1. Combined Assessment of Function and Survival Score (CAFS)

Multiple imputation analysis assuming MAR

The CAFS will be analyzed using missing imputation under MAR and ANCOVA. This endpoint will be analyzed using the FAS at weeks 24, 48, 72 and 96 (denoted below as week X).

Mitsubishi Tanabe Pharma America, Inc.

9.2.2.1.2. ALSFRS-R score - Changes from Baseline

The changes from baseline to (CHG) to all post-baseline visits throughout the periods of both MT-1186-A02 and MT-1186-A04 in ALSFRS-R will be included in a Mixed Model for Repeated Measures (MMRM) using SAS PROC MIXED. The model includes response data from all post-baseline visits with no imputation for missing data. The ALSFRS-R at baseline (BASE), randomization strata of ALSFRS-R rate of decline (DR) score during the screening period (2 levels strata of -1,-2 or -3,-4), Geographical Region (GR) (3 levels strata of Europe, America or Asia Pacific), Treatment Group (TRTP), Visit (AVISIT) and Treatment-by-Visit interaction will be included as fixed factors in the model. An unstructured covariance structure will be assumed, and the denominator degrees of freedom will be computed using the Kenward-Roger method. In case the model will not converge with the unstructured covariance structure, the heterogeneous compound symmetry (CSH) and the heterogeneous Toeplitz structure (TOEPH) will be used instead (in that order). The least-squares mean (LSMEANS) estimates for the mean change from baseline to Week 4 (A02), Week 8 (A02), Week 12 (A02), Week 24 (A02), Week 36 (A02), Week 48 (A02 and A04 Day1), Week 60 (A04 Week 12), Week 72 (A04 Week 24), Week 84 (A04 Week 36) and Week 96 (A04 Week 48), as well as the difference of the estimates between oral edaravone 105 mg daily versus oral edaravone 105 mg on/off regimen will be displayed with their corresponding standard errors, p-values, and 95% confidence interval. The same analysis will be conducted for each domain of ALSFRS-R. The SAS code planned for the primary analysis is outlined below.

9.2.2.1.3. Time to death, tracheostomy, or permanent assisted mechanical ventilation:

The secondary endpoint of time to death, tracheostomy, or permanent assisted mechanical ventilation (TIMETO2) will be analyzed similarly as the primary endpoint analysis using the stratified log rank (section 9.2.1.1).

[figure not shown]
Mitsubishi Tanabe Pharma America, Inc.

9.2.2.1.3.1. Supportive analysis for time to death, tracheostomy, or permanent assisted mechanical ventilation

- 1) Repeat the supportive analysis for the primary endpoint using Cox Proportional Hazard Model.
- 2) The restricted mean survival time (RMST) using non-parametric analysis, will be employed for time to death, tracheostomy, or permanent assisted mechanical ventilation (TIMETO2). The RMST will be plotted and compared between edaravone 105 mg once daily to edaravone 105 mg on/off. The following SAS code will be used with the maximum timeframe of 700 days:

3) Decomposition of the event analyzed in this secondary endpoint will be performed in an attempt to understand the effect on each event component separately. The time to death, time to permanent assisted mechanical ventilation and time to tracheostomy will be analyzed separately using a similar method as specified for the secondary in section 9.2.1.1.

Page 49 of 61

Mitsubishi Tanabe Pharma America, Inc.

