Change in ALSFRS-R score will be analyzed at all visits from baseline in Study MT-1186-A02 to the end of Study MT-1186-A04 using MMRM with terms for baseline ALSFRS-R score, Study MT-1186-A02 randomization strata, treatment, visit, and treatment-by-visit interaction. The unstructured covariance matrix will be used to model the within-subject errors. Denominator degrees of freedom will be estimated using Kenward-Roger's approximation. The least-squares mean estimates for the mean change at all visits from baseline in Study MT-1186-A02 to the end of Study MT-1186-A04, as well as the difference of the estimates between oral edaravone 105 mg daily versus oral edaravone 105 mg on/off regimen, will be displayed with their corresponding standard errors, p-values, and 95% CI.

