4.2. Sample Size and Power Considerations

In total, approximately 300 subjects who have successfully completed Study MT-1186-A02 are anticipated to be enrolled in this MT-1186-A04 study. A formal sample size calculation was not performed. However, data from 380 subjects (190 subjects per group) randomized in Study MT-1186-A02 will be included for all analyses. Hence, using MT-1186-A02 and MT-1186-A04 survival data and assuming 65% survival rate of the primary endpoint for the control group, the planned sample size of 190 subjects per group initially randomized in Study MT-1186-A02 will provide 70% power to detect a statistically significant result if the true hazard ratio between edaravone 105 mg daily (test) and edaravone 105 mg on/off regimen (control) in the primary endpoint is HR=0.775 (implying 22.5% risk reduction in the hazard due to daily treatment). This calculation of 70% power assumes a 2-sided alpha of 20% based on a rare disease condition (Hilgers RD et al., 201614) using the log-rank test and a follow-up time of up to 48 weeks in Study MT-1186-A04.

When this SAP version 1.0 was finalized and signed, for 384 subjects randomized in Study MT-1186-A02, 202 subjects who have successfully completed Study MT-1186-A02 were enrolled in this MT-1186-A04 study.

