7.2. Type I Error Control

Type I error will not be controlled for multiplicity adjustment between the primary endpoint and the secondary endpoints. All statistical tests for primary endpoint as well as for other endpoints will be done at 2-sided significance level with nominal values of 20% and 5%,

Mitsubishi Tanabe Pharma America, Inc.

respectively. Point estimates of treatment differences will be accompanied with 2-sided 80% and 95% confidence intervals where applicable respectively.

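### The ALSFRS-R MMRM gives baseline score and decline-rate stratum one fixed effect from Week 4 to Week 96; if either predicts slope, late-visit SEs are inflated, mostly as over-wide intervals

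*SAP*

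**What the plan says.** SAP Section 9.2.2.1.2 models change from baseline at ten visits, Week 4 to Week 96. The fixed terms are baseline ALSFRS-R, the two-level decline-rate stratum, the three-level region stratum, treatment, visit and treatment-by-visit: "Visit (AVISIT) and Treatment-by-Visit interaction will be included as fixed factors in the model". No other interaction is listed. Protocol Section 17.4.5.4 agrees: baseline score, then "Study MT-1186-A02 randomization strata, treatment, visit, and treatment-by-visit interaction".

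On the rest of the model the SAP states: "An unstructured covariance structure will be assumed, and the denominator degrees of freedom will be computed using the Kenward-Roger method". On missing visits: "The model includes response data from all post-baseline visits with no imputation for missing data". If the unstructured covariance fails to converge, two simpler structures follow in a set order. Estimates, standard errors, p-values and 95% intervals are to be shown at every visit. The same method is used for the ALSFRS-R domains and, with the relevant baseline value, for ALSAQ-40, %SVC and body weight. The SAP announces SAS code for this model, but the code does not appear in the public text.

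**The concern.** The stratum is a measure of slope: it groups subjects by ALSFRS-R decline during screening (-1,-2 against -3,-4). If any of that difference persists, the strata hardly differ in change from baseline at Week 4 and differ most at Week 96. The same holds for baseline score if it predicts slope. A single coefficient cannot follow this. With an unstructured covariance it is determined mainly by the early, less variable visits, so almost all of the late effect stays in the residual.

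What is at stake is how wide the displayed intervals are at late visits, where data are thin. SAP Section 4.2 reports, of 384 randomised, that "202 subjects who have successfully completed Study MT-1186-A02 were enrolled in this MT-1186-A04 study", which is 53%.

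**Working it through.** **The plan's own figure.** The only power figure in the documents is 70%, for the primary log-rank test. With exponential survival, control event-free probability is 0.65 at Week 48 and 0.65² = 0.4225 at Week 96. On the daily regimen it is 0.4225^0.775 = 0.513. Expected events are 190 × (0.5775 + 0.487) = 202.3. Power is Φ(√(202.3/4) × |ln 0.775| − 1.282) = Φ(0.531) = 0.702. The figure reproduces and does not involve the MMRM, for which no power or precision is stated.

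**Inputs for the MMRM check.** From the documents: 384 subjects, ten visits, the listed terms, unstructured covariance. Assumed, because the documents do not give them:
- mean decline 0.79 and slope SD 0.55 points per 4 weeks, chosen so that about 35% lose 12 points by Week 48, in line with the 65% event-free assumption;
- visit noise SD 1.5;
- 30% in the faster stratum;
- a range of slope effects.

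**Hand calculation, complete data.** Week 96 is 24 four-week units. Residual variance with nothing explained is 0.55² × 24² + 1.5² = 174.24 + 2.25 = 176.49, so SE ≈ √(176.49 × 4/384) = 1.356.
- A stratum gap of d per 4 weeks accounts for 0.3 × 0.7 × d² × 576. For d = 0.2 (0.05/week) this is 4.84, or 2.7% of the variance. For d = 0.4 (0.10/week) it is 19.35, or 11.0%.
- A baseline effect of g per 4 weeks per SD accounts for g² × 576. For g = 0.1 (0.025/week) this is 5.76, or 3.3%. For g = 0.2 (0.05/week) it is 23.04, or 13.1%.

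The SE ratio is √(176.49/(176.49 − explained)).

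**Simulation.** Each scenario used 150 replicates with no treatment effect. The model was fitted with the SAP's terms and again with both interactions. In the dropout runs, 52% were observed at Week 60 and 32% at Week 96. All figures are for Week 96; ratios are SAP model over interaction model.

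| Assumed slope effect | Hand SE ratio | Reported SE, complete | Reported SE, dropout | Empirical SD ratio, complete / dropout |
|---|---|---|---|---|
| Stratum 0.05/week | 1.014 | 1.348 / 1.328 = 1.015 | 1.448 / 1.428 = 1.014 | 0.998 / 0.999 |
| Stratum 0.10/week | 1.060 | 1.348 / 1.271 = 1.061 | 1.447 / 1.372 = 1.055 | 0.999 / 1.008 |
| Baseline 0.025/week per SD | 1.017 | 1.348 / 1.324 = 1.018 | 1.448 / 1.425 = 1.017 | 1.001 / 0.984 |
| Baseline 0.05/week per SD | 1.072 | 1.347 / 1.256 = 1.073 | 1.447 / 1.357 = 1.066 | 1.041 / 1.014 |
| Stratum 0.10 and baseline 0.025 | 1.080 | 1.347 / 1.247 = 1.080 | 1.446 / 1.348 = 1.072 | 1.003 / 1.000 |

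**Stratum.** Reported variance is too high by 1.014² − 1 = 2.8% up to 1.060² − 1 = 12%. The estimator itself hardly changes: empirical variance ratios run from 0.998² = 0.996 to 1.008² = 1.016. If the interaction-model SE is right, a nominal 5% test at a ratio of 1.055 has true size 2Φ(−1.96 × 1.055) ≈ 3.9%. A second simulation, with slope SD 0.13 points/week, residual SD 1.8 and 40% in the faster stratum, gave reported variance cuts of about 2.5% and 12% for the same gaps and true cuts of about 1% and 3%. An analytic version with dropout unrelated to stratum put the true cut at no more than 0.5%.

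**Baseline.** Chance imbalance between arms is not controlled by design, so reported and true loss should be similar. The second simulation found this: about 3–5% and 12–15% of variance for 0.025 and 0.05 points/week per SD. The empirical SDs in the table are noisier. With 150 replicates each has a relative standard error of about 1/√(2 × 149) = 5.8%; pairing reduces but does not remove this. They show 1.041² − 1 = 8% on complete data and 1.014² − 1 = 3% with dropout for the larger effect, and nothing reliable for the smaller one.

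**Combined case.** With dropout, the 95% half-width is 1.96 × 1.446 = 2.83 points against 1.96 × 1.348 = 2.64. Mean treatment estimates from the two models agreed within 0.04 points in every scenario.

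**The case against.** The strongest reply is that stratified randomisation has already secured the benefit of the decline-rate factor, so leaving out its visit interaction costs the estimator almost nothing and errs on the safe side. For the stratum this stands. A reader might infer that collected prognostic information is being wasted on a large scale, for example a 22% variance saving at a stratum gap of 0.15 points/week. The documents do not support that, for two reasons. First, the saving is in reported, not true, variance. Second, the gap is too large. The screening bands differ by about 2 points, while the difference of two ratings with noise SD 1.8 has SD 1.8 × √2 = 2.5, so regression to the mean is strong. Simulated true gaps were about 0.03 to 0.08 points/week for assumed screening lengths of 6 to 24 weeks. The documents do not give the screening length. On these inputs 0.10 is already generous.

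Two further replies stand as limits. The size rests on assumed inputs throughout. The analysis is also secondary: its p-values are nominal and unordered, the extension was stopped, and no final analysis is planned. A reader might also infer a biased treatment effect or a weakened primary analysis. Neither follows: the estimates agree, and the log-rank and Cox analyses do not use this model.

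The SAS code cannot be seen and may contain the interactions. That does not settle the matter, because the written specification in both documents does not.

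**Conclusion.** The point holds as a minor one about efficiency and calibration. As written, baseline score and decline-rate stratum are held to a constant effect over 96 weeks. If either predicts slope, late-visit residual variance is inflated. For the stratum, the effect is mainly intervals about 1% to 6% too wide and conservative tests, for assumed gaps of 0.05 to 0.10 points/week. For baseline score, some real precision is lost: a few percent of variance for a weak association with slope, and perhaps 3% to 15% for a stronger one, with the calculations disagreeing within that range. These sizes depend on the assumed slope SD, noise SD, stratum share and dropout pattern. The direction depends only on one of the two variables predicting rate of decline. Nothing here shows bias or an anticonservative test.

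**What to change.** In SAP Section 9.2.2.1.2, add baseline ALSFRS-R-by-visit and decline-rate-stratum-by-visit to the fixed terms. Add the matching baseline-by-visit and stratum-by-visit terms to the MMRMs for the ALSFRS-R domains, ALSAQ-40, %SVC and body weight. Check the SAS MODEL statements against the revised text; if the code already has these terms, correct the text only.

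The cost is 2 × (10 − 1) = 18 mean parameters with up to 384 subjects (6 for ALSAQ-40, which has four visits), and no new data. The downside is a few degrees of freedom and a slightly higher chance of non-convergence at sparse late visits, for which the SAP already has a fallback order. SAP Section 2 allows updates during the study. The change should be made before the database lock that feeds the analysis and without sight of results by arm. After that point, run the interaction model as a labelled supplementary analysis, which both documents leave room for.
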